## ***INTRODUCTION***

This Statistical Analysis Plan for the Myocardial Ischemia and Transfusion (MINT) trial is consistent with and expands upon the statistical methods outlined in the trial protocol. This document includes 1) a brief summary of the MINT trial design, 2) the trial aims, 3) definitions of the specified MINT trial outcomes, 4) the original sample size and power calculations, 5) the interim monitoring plan, 6) analytic approach, and 7) proposed template tables and figures.

### ***1. TRIAL DESIGN***

#### **Study Design**

The MINT trial is a randomized, open-label, multicenter clinical trial designed to determine whether a liberal transfusion strategy with a threshold of 10 g/dL reduces the composite outcome of all-cause mortality or nonfatal myocardial reinfarction through 30 days, compared with a restrictive transfusion strategy with a threshold of 7 to 8 g/dL among patients with an acute myocardial infarction and a hemoglobin concentration less than 10 g/dL. The trial is conducted in approximately 144 clinical sites in the United States, Canada, France, Brazil, New Zealand, and Australia. The two transfusion strategies are allocated with a 1:1 ratio using a permuted block design, with random variable block sizes, stratified by clinical site.

#### **Population**

The eligible study population includes adult patients with ST-segment elevation myocardial infarction or non ST-segment elevation myocardial infarction consistent with the 3rd Universal Definition of Myocardial Infarction criteria that occurs on admission or during the index hospitalization, and anemia defined as a hemoglobin concentration less than 10 g/dL at the time of randomization. Patients with Type 1, Type 2,

Type 4b, and Type 4c are eligible, and the occurrence of the index MI is determined by the enrolling site study team.

## **Trial Transfusion Strategies**

The trial compares a restrictive and a liberal approach to transfusion therapy. The transfusion strategy is followed during the index hospitalization from the time of randomization up to 30-days post-randomization, hospital discharge, or death, whichever comes first.

Restrictive Transfusion Strategy: Patients randomized to the restrictive transfusion strategy may receive a transfusion if the hemoglobin concentration falls below 8 g/dL and are strongly encouraged to receive transfusion if the hemoglobin concentration is below 7 g/dL. Transfusion is also allowed when anginal symptoms are determined by the patient's treating physician to be related to anemia and are not controlled with anti-anginal medications. Enough blood is given to increase the hemoglobin concentration to above 7 to 8 g/dL or to relieve anginal symptoms. A post transfusion hemoglobin measurement is required.

Liberal Transfusion Strategy: Patients randomly allocated to the liberal transfusion strategy receive one unit of packed RBCs following randomization and will receive enough blood to raise the hemoglobin concentration to 10 g/dL or above any time during the index hospitalization that the hemoglobin concentration is detected to be below 10 g/dL. A post transfusion hemoglobin measurement showing a hemoglobin level of at least 10 g/dL must be obtained.

For both strategies, blood is administered one unit at a time followed by a hemoglobin measurement. A patient in either group may be transfused at any time without a hemoglobin level if the patient is actively bleeding (e.g., brisk gastrointestinal bleeding) and the treating physician believes an emergency transfusion is needed. A patient in either group with history of congestive heart failure or low ejection fraction may receive diuretics prior to or after transfusion and transfusion may be delayed until the patient can safely tolerate the additional volume. Patients with end stage renal disease may receive transfusion during dialysis if requested by treating physician. The transfusion protocol is suspended for 24 hours if the patient goes to surgery.

## **Assessments of laboratory markers**

The trial collects hemoglobin and troponin levels and electrocardiogram (ECG) readings at specified time points while the patient is in the hospital. The required collection time points for hemoglobin levels and

ECGs are within 24 hours prior to randomization, and on days 1, 2 and 3 post-randomization. The required time points for the troponin levels are within 24 hours prior to randomization and post randomization, at 12 hours, and on days 1, 2 and 3. All hemoglobin and troponin levels performed for during the index hospitalization are collected by the trial.

## **Participant Follow-up**

At hospital discharge, death or 30 days post randomization, whichever comes first, the study staff submit data related to the hospitalization including health status, laboratory results, blood transfusions, and post randomization clinical events. Study staff contact the patient at 30 days post-randomization to ascertain vital status, administer the quality-of-life questionnaire, and determine if there has been a subsequent hospital admission or emergency room visit. Study staff obtain and review the medical records for each readmission and record relevant data and study outcomes. If an acute coronary syndrome event is suspected from the time of randomization until 30-days post-randomization, the staff submits documentation for central review. Study staff contact participants at 6 months following randomization to ascertain the patient's vital status.

Recurrent myocardial infarction is diagnosed when a suspected myocardial ischemic event is reported by the investigators at the clinical sites and confirmed by the Clinical Event Committee. In addition to adjudication of site suspected events, the trial has a surveillance process in which all cardiac troponin values are reviewed by the Clinical Event Committee to detect abnormal biomarker patterns. When criteria are met, the Clinical Event Committee requests that the site submit medical records and ECGs that are temporally related to the abnormal values. The Clinical Events Committee adjudicates occurrences of myocardial infarction, masked to assigned transfusion strategy, from randomization through 30-days post-randomization. Myocardial infarction is classified according to MI type as specified in the 3rd Universal Definition of Myocardial Infarction and whether MI type was ST segment elevation MI (STEMI) non-ST segment elevation MI (NSTEMI), or cannot be determined.

## **2. TRIAL AIMS**

### **Primary Aim**

The MINT primary aim is to determine whether a liberal transfusion strategy with a threshold of 10 g/dL reduces the composite outcome of all-cause mortality or nonfatal myocardial reinfarction through 30 days following randomization, compared to a restrictive transfusion strategy with a threshold of 7 to 8 g/dL among patients with an acute myocardial infarction and a hemoglobin concentration less than 10 g/dL.

## **Secondary Aims**

- 1) To determine whether a liberal (10g/dL) transfusion strategy reduces all-cause mortality within 30 days, compared to a restrictive transfusion strategy.
- 2) To determine whether a liberal (10g/dL) transfusion strategy reduces myocardial reinfarction within 30 days, compared to a restrictive transfusion strategy.
- 3) To determine whether a liberal (10g/dL) transfusion strategy reduces the composite outcome of all-cause mortality, nonfatal myocardial reinfarction, ischemia driven unscheduled coronary revascularization (percutaneous coronary intervention or coronary artery bypass grafting), or readmission to the hospital for ischemic cardiac diagnosis within 30 days, compared to a restrictive transfusion strategy.

## **Tertiary Aims**

- 1) To determine whether a liberal (10g/dL) transfusion strategy reduces all-cause mortality, nonfatal myocardial reinfarction, or unstable angina (i.e. acute coronary syndrome) within 30 days, compared to a restrictive transfusion strategy.
- 2) To determine whether a liberal (10g/dL) transfusion strategy reduces ischemia driven unscheduled coronary revascularization within 30-days compared to a restrictive strategy.
- 3) To determine whether a liberal (10g/dL) transfusion strategy reduces unscheduled readmission to hospital for ischemic cardiac diagnosis within 30 days, compared to a restrictive strategy.
- 4) To determine whether a liberal (10g/dL) transfusion strategy increases congestive heart failure within 30 days, compared to a restrictive transfusion strategy.
- 5) To determine whether a liberal (10g/dL) transfusion strategy reduces unscheduled readmission to hospital for any reason within 30 days, compared to a restrictive strategy.
- 6) To determine whether a liberal (10g/dL) transfusion strategy increases each of the individual thrombotic/hemorrhagic outcomes of stroke, pulmonary embolism or deep venous thrombosis, and bleeding within 30 days, compared to a restrictive strategy.

- 7) To determine whether a liberal (10g/dL) transfusion strategy increases each of the individual infectious outcomes of pneumonia, blood stream, and urinary tract within 30 days, compared to a restrictive strategy.
- 8) To determine whether a liberal (10g/dL) transfusion strategy reduces each of the individual in-hospital outcomes of length of hospital stay post randomization and number of days in intensive care unit, compared to a restrictive strategy.
- 9) To determine whether a liberal (10g/dL) transfusion strategy increases patient reported quality of life using the EuroQol questionnaire (EQ-5D) at 30 days compared to a restrictive strategy
- 10) To determine whether a liberal (10g/dL) transfusion strategy reduces all-cause mortality at 6-months following randomization, compared to a restrictive strategy.

### **3. DEFINITIONS OF OUTCOMES**

Myocardial Reinfarction: Myocardial reinfarction will be classified by the Clinical Events Committee using 3rd Universal Definition of MI definition. Patients with reinfarction will need to demonstrate a fall in the troponin value and then a subsequent rise of at least 20% with additional evidence (new ECG changes, imaging evidence, clinical history) as in the MI definition to diagnose a new event. Myocardial infarction is classified according to MI type and whether MI type was STEMI, NSTEMI, or cannot be determined.

Death and Cause of Death: For each death, the cause will be determined by the site personnel into one of three categories: cardiac death (e.g., congestive heart failure, dysrhythmia), noncardiac death (e.g., infection, cancer), or undetermined cause of death. Information about the specific cause of death will also be collected.

Unscheduled Coronary Revascularization (unstaged): Ischemia driven, unscheduled coronary revascularization (coronary artery bypass surgery or PCI) within 30 days of randomization will be recorded by the sites. Prior to randomization, the site will record if a coronary revascularization is planned (staged). All coronary revascularization procedures will be recorded, but an elective planned staged procedure will not be included as an outcome. Information about the reason for the procedure will also be collected to ensure that the revascularization was done to treat ischemic heart disease.

Readmission to Hospital, Overall and for Primary Cardiac Diagnosis: All re-admissions to the hospital that had not been planned prior to randomization will be captured, and the primary diagnosis for each

hospitalization will be classified as: ischemic cardiac diagnosis (e.g., myocardial infarction, unstable angina), non-ischemic cardiac diagnosis (e.g. heart failure) or non-cardiac.

Unstable Angina: The MINT trial sites will use 2014 ACC/AHA Key Data Elements and Definitions for Cardiovascular Endpoint Events in Clinical Trials to define unstable angina. To diagnose unstable angina requires that four criteria be met: 1) worsening ischemic discomfort, 2) unscheduled hospitalization, 3) negative cardiac biomarker, 4) objective evidence of myocardial ischemia.

Congestive Heart Failure: Sites personnel will use 2014 ACC/AHA Key Data Elements and Definitions for Cardiovascular Endpoint Events in Clinical Trials to define congestive heart failure. New or worsening symptoms of congestive heart failure on presentation (increasing dyspnea, paroxysmal nocturnal dyspnea, orthopnea), has objective evidence of new or worsening heart failure, and receives initiation or intensification of treatment specifically for heart failure.

TIA or Stroke: The 2014 ACC/AHA Key Data Elements and Definitions for Cardiovascular Endpoint Events in Clinical Trials will be used to define stroke. A transient ischemic attack (TIA) is defined as “a transient episode of focal neurological dysfunction caused by brain, spinal cord, or retinal ischemia, without acute infarction.” Stroke is defined on the basis of the presence of acute infarction as demonstrated by imaging or based on the persistence of symptoms more than 24 hours.

Deep Venous Thrombosis or Pulmonary Embolism: Deep vein thrombosis will be diagnosed if duplex ultrasound, magnetic resonance venogram (MRV), or venogram is definite or probable positive. Site investigators will record if location is proximal or distal. Pulmonary embolism will be diagnosed with a high probability ventilation perfusion lung scan, CT scan, or pulmonary angiogram.

Bleeding: Major bleeding will be defined as 1) fatal bleeding, and/or 2) symptomatic bleeding in a critical area or organ, such as intracranial, intraspinal, intraocular, retroperitoneal, intra-articular or pericardial, or intramuscular with compartment syndrome, and/or 3) bleeding causing a drop in hemoglobin concentration of 2 g/dL or greater from the last hemoglobin concentration prior to randomization to the nadir hemoglobin concentration during hospitalization or up to 30 days post randomization. The drop in

hemoglobin concentration will account for each unit of red blood cell transfusion transfused by subtracting 1 g/dL for each unit administered.

Infections recorded include pneumonia and blood stream infections.

Pneumonia: Pneumonia will be diagnosed using CDC criteria which includes radiographic abnormalities and combination of symptoms (i.e., cough), signs (i.e., fever, tachypnea, or laboratory abnormalities (i.e., white blood cell count, hypoxemia).

Blood Stream Infection: Blood stream infection will be defined using CDC criteria which includes a recognized pathogen cultured from 1 or more blood cultures and organism cultured from blood is not related to an infection at another site, at least 1 of the following signs or symptoms: fever, chills, or hypotension and signs and symptoms and positive laboratory results are not related to an infection at another site and common skin contaminant is cultured from 2 or more blood cultures drawn on separate occasions.

Length of Stay and Intensive Care Unit Days: The trial records the number of days post randomization that the patient is in the hospital and in intensive care unit.

Quality of Life: The EuroQol questionnaire (EQ-5D), a standardized instrument that measures health related quality of life in 5 dimensions: mobility, self-care, usual activities, pain/discomfort and anxiety/depression, is used as a measure of patient perceived global health status 30 days after randomization. The EQ-5D utility index value and health today scores will be reported.

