Deep vein thrombosis will be diagnosed if duplex ultrasound, magnetic resonance venogram (MRV), or venogram is definite or probable positive. Site investigators will record if location is proximal or distal. Pulmonary embolism will be diagnosed with a high probability ventilation perfusion lung scan, CT scan, or pulmonary angiogram.

ix Bleeding

Major bleeding will be defined as 1) fatal bleeding, and/or 2) symptomatic bleeding in a critical area or organ, such as intracranial, intraspinal, intraocular, retroperitoneal, intra- articular or pericardial, or intramuscular with compartment syndrome, and/or 3) bleeding causing a drop in hemoglobin concentration of 2 g/dL or greater (62) from the last hemoglobin concentration prior to randomization to the nadir hemoglobin concentration during hospitalization or up to 30 days post randomization. The drop in hemoglobin concentration will account for each unit of red blood cell transfusion transfused by subtracting 1 g/dL for each unit administered.

x Infections

x.1 Pneumonia

Pneumonia will be diagnosed using CDC criteria (48) which includes radiographic abnormalities and combination of symptoms (i.e., cough), signs (i.e., fever, tachypnea, or laboratory abnormalities (i.e., white blood cell count, hypoxemia).

x.2 Blood Stream Infection

Blood stream infection will be defined using CDC criteria which includes a recognized pathogen cultured from 1 or more blood cultures and organism cultured from blood is not related to an infection at another site, at least 1 of the following signs or symptoms: fever, chills, or hypotension and signs

and symptoms and positive laboratory results are not related to an infection at another site and common skin contaminant is cultured from 2 or more blood cultures drawn on separate occasions.

x.3 Urinary Tract Infection

Urinary Tract Infection will be defined using CDC criteria (48) which include one of the following signs or symptoms: fever (>38.0°C) or localized pain or tenderness, and laboratory evidence for infection.

xi Length of Stay and Intensive Care Unit Days

The trial will collect the number of days post randomization that patient is in the hospital and in intensive care unit.

xii Quality of Life

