Baseline demographic (e.g., age, gender, race), co-morbidity (e.g. cardiovascular risk factors), characteristics of cardiac disease (e.g., left ventricular function, number of coronary vessels obstructed), renal disease, and medications (e.g., aspirin, P2Y12 receptor inhibitor, anticoagulant, beta-blocker statins) will be collected to reflect patient status at the time of randomization. Characteristics describing the study intervention including red blood cell transfusion information (e.g. expiration date, leukoreduction, storage solution, ABO) will be recorded. In hospital, hemoglobin levels and the number and timing of transfusions will be recorded for the two assigned transfusion strategies.

F Statistical Plan

F1 Sample Size Determination and Power

In the MINT pilot trial, the composite 30-day rate of death and myocardial infarction was 16.4%. Higher rates were observed in the Kaiser System preliminary data. Thirty-day rates of 16.4%, 18%, or 20% are reasonable for this trial since the proposed study population will not exclude the sickest patients as was done in the MINT pilot study. Using a two-sided inequality test and a simple chi-square statistic with alpha=0.05, we determined the samples sizes required to provide 80% and 90% power to detect varying relative reductions in the 30-day event rates for death and myocardial infarction between the two assigned treatment groups. Based on these estimates, we plan to enroll a sample of 3500 patients. If the rate of missing outcome data is no more than 5%, the trial would have 3324 patients with analyzable outcome data at 30-days. Assuming an overall event rate of 16.4%, the trial will have 80% power to detect a 20% relative reduction (i.e. 18.2% vs. 14.6%) and >90% power to detect a 20% relative reduction (i.e. 22.2% vs. 17.8%). We also performed

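### The hemoglobin criterion for major bleeding does not say what the 1 g/dL per unit is subtracted from or which units count, so equal blood loss can be classified differently by arm.

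*SAP*

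**What the plan says.** SAP section 3 (Bleeding) and Protocol E7 7.a ix give the same three-part definition. The first two parts use no hemoglobin value: "Major bleeding will be defined as 1) fatal bleeding, and/or 2) symptomatic bleeding in a critical area or organ". The third is "bleeding causing a drop in hemoglobin concentration of 2 g/dL or greater", measured "from the last hemoglobin concentration prior to randomization to the nadir hemoglobin concentration during hospitalization or up to 30 days post randomization". The SAP then adds that the drop in "hemoglobin concentration will account for each unit of red blood cell transfusion transfused by subtracting 1 g/dL for each unit administered", and the protocol has the same sentence. Neither document states what the 1 g/dL is subtracted from, and neither limits the units by when they were given.

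The arms differ by design in units given. Under SAP Trial Transfusion Strategies, liberal patients "receive one unit of packed RBCs following randomization and will receive enough blood to raise the hemoglobin concentration to 10 g/dL or above". Restrictive patients "may receive a transfusion if the hemoglobin concentration falls below 8 g/dL", and transfusion is strongly encouraged below 7 g/dL. Protocol E8 says that in hospital "the number and timing of transfusions will be recorded for the two assigned transfusion strategies".

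Bleeding within 30 days belongs to tertiary aim 6, which asks whether liberal transfusion increases it. Under the SAP's analysis of secondary and other outcomes it is tested for superiority and, failing that, for non-inferiority of the restrictive strategy at a risk ratio of 1.15.

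**The concern.** Some adjustment for transfusion is needed: without it, units given before the nadir would mask blood loss, mostly in the liberal arm. As worded, however, the adjustment has two plausible readings, and neither is neutral between the arms.

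- **Subtract from the drop (the literal grammar).** Each unit makes the drop smaller, so a patient who bled and was transfused appears to have bled less. The loss of events falls mainly on the liberal arm.
- **Subtract from the nadir.** Each unit makes the drop larger, which is the right sign. But a unit given after the nadir did not affect that value, and as written it still counts. The gain in events falls mainly on the liberal arm.

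What is at stake is the answer to tertiary aim 6. The nadir reading pushes the restrictive/liberal ratio below 1, which favors both a superiority and a non-inferiority conclusion for restrictive. The literal reading pushes it the other way and discards real bleeds.

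**Working it through.** The documents give no event rate or power figure for bleeding, so there is no stated number to reproduce.

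**1. Formulas.** Let B be the last pre-randomization hemoglobin, N the nadir, U all units given and U* the units given between the B and N samples.

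- Literal reading: (B - N) - U
- Nadir reading, all units: (B - N) + U
- Nadir reading, windowed: (B - N) + U*

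**2. Two worked patients.** Assume that each unit raises hemoglobin by 1 g/dL, B = 9.2, and the liberal patient gets the mandated unit first (9.2 + 1 = 10.2) and then bleeds.

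- *True loss 1.1.* Liberal: N = 10.2 - 1.1 = 9.1, then one more unit, so U = 2 and U* = 1. Restrictive: N = 9.2 - 1.1 = 8.1, no units.
- *True loss 2.1.* Liberal: N = 10.2 - 2.1 = 8.1, then two more units, so U = 3 and U* = 1. Restrictive, with a clinician who transfuses only below 7: N = 9.2 - 2.1 = 7.1, no units.

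| True loss | Arm | B - N | Literal | All units | Windowed |
|---|---|---|---|---|---|
| 1.1 | Liberal | 0.1 | -1.9 | 2.1 (major) | 1.1 |
| 1.1 | Restrictive | 1.1 | 1.1 | 1.1 | 1.1 |
| 2.1 | Liberal | 1.1 | -1.9 | 4.1 (major) | 2.1 (major) |
| 2.1 | Restrictive | 2.1 | 2.1 (major) | 2.1 (major) | 2.1 (major) |

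The all-units version adds a liberal event at a loss of 1.1. The literal version removes a liberal event at a loss of 2.1. The windowed version returns the true loss in all four rows.

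**3. Simulation of patients with a noted bleed.** There were 30,000 patients per arm and scenario. Assumptions, none from the documents: B uniform on 7-9.9; one bleed on day 1-4; exponential loss with mean 0.8 or 1.2 g/dL, the same in both arms; rise of 1 g/dL per unit; measurement SD 0.2; restrictive transfused below 8 or below 7. The true share losing at least 2 g/dL is exp(-2/0.8) = 8% or exp(-2/1.2) = 19%.

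- All units: liberal 60-68%, restrictive 22-51%; restrictive/liberal ratio about 0.4-0.7 (truth 1.0). True losses of 2 g/dL or more were caught in about 99-100% of both arms.
- Literal: liberal 0%, restrictive 0-4%.
- Windowed: ratio 1.02-1.14.

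**4. Second simulation, fixed losses.** There were 8,000 patients per arm; B normal with mean 8.6 and SD 0.8, limited to 6-9.9; measurement SD 0-0.5. Share meeting the numeric criterion:

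| True loss | Rule | Liberal | Restrictive <8 | Restrictive <7 |
|---|---|---|---|---|
| 1.0 | All units | 76-84% | 42-65% | 12-34% |
| 2.5 | All units | 98-100% | 98-100% | 98-100% |
| 2.5 | Literal | 0% | 0-1.5% | 12-15% |

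With the windowed rule, a loss of 1.0 gave liberal 0-3.5% and restrictive 0-4.9%; a loss of 2.5 gave liberal 82-98% and restrictive 88-100%.

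**5. Dependence on the rise per unit.** If a unit truly raises hemoglobin by r, the windowed drop at the sample after the bleed equals true loss + U*(1 - r). With U* = 2 the error is 2 x (1 - 0.8) = +0.4 at r = 0.8 and 2 x (1 - 1.2) = -0.4 at r = 1.2. In simulation at r = 0.8 the windowed ratio was 0.80-0.90. Taking the largest adjusted drop over all samples is more sensitive: about 0.5-0.7 at r = 0.8 and 1.2-1.65 at r = 1.2.

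**The case against.** The strongest reply is that the drop is defined as ending at the nadir, so the units to account for are naturally those given up to the nadir, and counting later units is inferred from silence. That is a sensible reading and may be what was meant. But the text refers to each unit administered, sets no window, and uses a verb that literally gives the opposite sign. An analyst working from these sentences could program any of the three formulas.

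A reader might infer that the bleeding rate reflects the assigned strategy instead of bleeding. The documents do not support that. The first two criteria use no hemoglobin or transfusion data, and the third requires bleeding as the cause. With all units added, true losses of 2 g/dL or more are caught almost completely in both arms, so the distortion under that reading lies in noted bleeds below 2 g/dL. A reader might also infer that the bias always runs against the liberal arm. It does not; its direction reverses between the two readings.

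The requirement that bleeding be the cause limits the problem but does not remove it, because once a bleed is noted the adjusted drop decides whether it is major. The Clinical Events Committee is described as adjudicating myocardial infarction; neither document describes masked review of bleeding.

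Two further points stand. Bleeding is one of many tertiary outcomes, to be interpreted as such, and the primary and secondary outcomes are untouched. And the simulated ratios cover the third criterion only, among patients already assumed to have a noted bleed; they do not predict the trial's overall bleeding ratio.

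**Conclusion.** The concern holds as a defect in the third criterion. The sign and the time window of the adjustment are undefined, and because the arms differ by design in units given, the same loss can be major in one arm and not in the other. That conclusion needs only the definition and the two transfusion rules. The size (restrictive/liberal ratio about 0.4-0.7 with all units counted, near-total loss of events under the literal reading) depends on the assumed hemoglobin distribution, size of bleeds, rise per unit and restrictive threshold used.

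The windowed rule removes most of the difference but is not perfect. It is neutral only so far as a unit raises hemoglobin by 1 g/dL. It can also miss a bleed when the lowest value precedes it. For example, a liberal patient goes from 6.9 to 7.9 after the first unit and to 10.9 after three more, then loses 2.5 and reaches 8.4. The nadir stays at 7.9, and the windowed drop is 6.9 - 7.9 + 1 = 0. The largest-value-over-all-samples rule would catch this case, but it over-counts through measurement noise (11% against a true 8%, and 23% against 19%, even at a rise of exactly 1 g/dL) and is more sensitive to the assumed rise. It is therefore not the better primary definition.

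**What to change.** Reword the third criterion identically in SAP section 3 and Protocol E7 7.a ix:

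- The adjusted drop is the last pre-randomization hemoglobin minus the nadir, plus 1 g/dL for each red cell unit given between those two samples.
- Units given after the nadir sample are not counted.
- Documented bleeding as the cause is still required.

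Add two sensitivity analyses: bleeding defined by the first two criteria only, which is free of the problem; and the full definition with other assumed rises per unit, for example 0.8 and 1.2 g/dL.

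The cost is a rewritten sentence in each document and a short derivation program, settled before the outcome is analyzed by arm. In-hospital hemoglobin values and transfusion timing are already collected. The window runs to 30 days, however, and for readmissions the documents promise only relevant data from the medical records, so the timing of units given during readmissions must be confirmed from those records.
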